6.4. WINDOWING CONVENTIONS

No visit windowing will be performed for this study at this time.

6.5. STATISTICAL TESTS

The main purpose of this phase Ib/II study consists in providing accurate estimates of clinically relevant variables and measures.

The two tailed 95% confidence intervals of the primary endpoint will be computed using the Normal Approximation or exact method (as applicable) for proportions. Confidence intervals for model parameters will be based on either the profile likelihood function. All tests will be two-sided, unless otherwise specified in the description of the analyses.

Document: PPD

Author: PPD

Version Number:

V2.2

Version Date:

21 March 2018

Template No: CS_TP_BS016 – Revision 3

Reference: CS_WI_BS005

Effective Date: 01May2012

Copyright © 2012 Quintiles Transnational Corp. All rights reserved.

The contents of this document are confidential and proprietary to Quintiles Transnational Corp. Unauthorized use, disclosure or reproduction is strictly prohibited.

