3.5. DETERMINATION OF SAMPLE SIZE

A standard 3+3 design adopting a modified Fibonacci escalation schema is used in **Part A** [3, 4, 5].

Sample size for **Part B** is discussed for the primary endpoint defined as the Overall Response Rate after 3 cycles. Simon's 2-stage design is employed in **Part B** [6] with the aim of testing the "null hypothesis" that $RR \leq 0.50$ versus the "alternative" that $RR \geq 0.75$. Response rate was assessed as defined in paragraph 6.2.5.2 of the Study protocol version 3.0. Overall, up to 28 patients are to be recruited, 12 patients being enrolled in Stage 1. PV patients enrolled at the MTD in **Part A** can be counted towards Stage 1.

Under the "null hypothesis" (if $RR = 0.50$), the expected total sample size is 18.2 patients, the probability of early termination at the end of Stage-1 is 0.613 and the probability of rejecting the "null hypothesis" is 0.081 (the target for the type-I error being 0.100).

Under the "alternative hypothesis" (if $RR = 0.75$), the probability of rejecting the "null hypothesis" in favor of the "alternative" is 0.902 (the type-II error being 0.098).

After testing the treatment on 12 patients in Stage 1, if 6 or fewer patients responded to the treatment, the trial should be terminated rejecting the "alternative" that $RR \geq 0.75$. Otherwise, the trial should go on to Stage 2 enrolling a further 16 patients to a total of 28 patients.

If at the end of Stage-2, a total of 17 or fewer patients responded to the treatment, the "alternative hypothesis" that $RR \geq 0.75$ should be rejected; alternatively, if 18 or more patients responded, the "null hypothesis" that $RR \leq 0.50$ should be rejected.

Estimations were obtained from CRO proprietary software (based on SAS® 9.2) according to the

Document: PPD

Author: PPD

Version Number:

V2.2

Version Date:

21 March 2018

Template No: CS_TP_BS016 – Revision 3

Reference: CS_WI_BS005

Effective Date: 01May2012

Copyright © 2012 Quintiles Transnational Corp. All rights reserved.

The contents of this document are confidential and proprietary to Quintiles Transnational Corp. Unauthorized use, disclosure or reproduction is strictly prohibited.

algorithm proposed by R. Simon [6].

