4. PLANNED ANALYSES

The following analyses are planned:

- A. Part A: Analyses to determine the Maximum Tolerated Dose (MTD);
- B. Part B (I): Stage 1 (Interim Analysis) of the Simon's 2-stage design (Primary evaluation of Response Rate)

Interim analysis will be performed on the 12 patients of the first stage of part B. If seven or more responses will be observed in the first stage of part B, further 16 patients will be enrolled in the second stage of part B. If six or fewer responses will be observed during the first stage then the study will be stopped. Futility will be assessed in 12 patients after 3 cycles.

The Interim analysis will evaluate preliminary efficacy and safety and tolerability of Givinostat at the MTD after 3 cycles in 12 patients. Exploratory endpoints analysis will also be included with available data after 3 cycles.

- C. Part B (II): Stage 2 (Overall Analysis) of the Simon's 2-stage design (at the end of Part B).

Final analysis will be performed in all 28 patients enrolled in two stages of part B after 6 cycles.

No formal DB lock is planned neither for the 1st Cycle of Part A nor for Stage 1 (Simon's 2-Stage design) of Part B of the study.

Three different Output Templates will be presented for the 3 sets of analyses.

Document: PPD

Author: PPD

Version Number:

V2.2

Version Date:

21 March 2018

Template No: CS_TP_BS016 – Revision 3

Reference: CS_WI_BS005

Effective Date: 01May2012

Copyright © 2012 Quintiles Transnational Corp. All rights reserved.

The contents of this document are confidential and proprietary to Quintiles Transnational Corp. Unauthorized use, disclosure or reproduction is strictly prohibited.

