Frequency and percentage of patients in each response category (CR, PR, no response (NR) for PV and ET; CR, major response, moderate response, minor response and NR rate for MF) will be presented at Cycle 3 Day 28 (C3D28). Of note, patients who dropped the study due to drug-related TEAE(s) before that the post-baseline efficacy measurement is obtained (i.e. at C3D28 and/or at C6D28), the post-baseline efficacy measurements (i.e. at C3D28 and/or at C6D28) will be considered as "No Response*", even if these assessments were not performed. "*" will allow to distinguish them from them from the therapeutic response evaluation result of "No Response", that will be reported without "*" (i.e. "No Response"). Other missing data will not be replaced, if not otherwise specified.

For **Part B** – Stage 1, Simon's design hypothesis will be evaluated by calculating the frequency and 95% CI of patients with a CR and/or PR at C3D28.

For Part B – Stage 2, the efficacy of Givinostat will be evaluated by means of a generalized linear model (logit link function and binomial distribution) adjusting for age, sex and disease type (PV, ET, MF). The therapeutic response will be collapsed in two categories in order to improve the model performance:

- For PV and ET:
 - a) "Responders" (i.e. CR and PR), and
 - b) "Not Responders" (i.e. NR);
- For MF:
 - a) "Responders" (i.e. CR, major response, moderate response and minor response), and
 - b) "Not Responders" (i.e. NR for MF).

In addition, the following primary safety parameters will be evaluated in **Part B after 3 cycles of treatment** (i.e. at the end of Cycles 3, or including data related to Cycles 1, 2 and 3) based on SAF analysis set:

- Number of patients experiencing AEs.
- Type, incidence, and severity of treatment-related AEs, graded according to CTCAE v. 4.03 (14th June 2010).

AEs will be coded using MedDRA dictionary (using the 20.1 version). AEs will be reported on a per patient basis. If a patient has more than one AE for a treatment that is coded to the same PT, the patient will be counted only once for that PT. Similarly, if a patient has more than one AE for a treatment within a SOC category, the patient will be counted only once in that SOC category. A patient with multiple CTCAE grades for an AE will be summarised under the maximum CTCAE grade recorded for the event.

Document: PPD

Author: PPD

Version Number:

V2.2

Version Date:

21 March 2018

Template No: CS_TP_BS016 – Revision 3

Reference: CS_WI_BS005

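### The final Part B 3-cycle response rate is to be reported with one-sample methods that ignore the futility stop: n/N is slightly biased, in a direction that depends on the viewpoint, and the permitted normal-approximation interval under-covers

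*SAP*

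**What the plan says.** SAP section 3.5 sets a Simon two-stage design for Part B: "Overall, up to 28 patients are to be recruited, 12 patients being enrolled in Stage 1", and "if 6 or fewer patients responded to the treatment, the trial should be terminated". Section 4 repeats the rule and ties it to response after 3 cycles: "If six or fewer responses will be observed during the first stage then the study will be stopped". With 7 or more responders a further 16 patients are enrolled. At the end the drug fails if "a total of 17 or fewer patients responded to the treatment", and 18 or more of 28 reject the null.

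On estimation, section 6.5 states the aim: "The main purpose of this phase Ib/II study consists in providing accurate estimates of clinically relevant variables and measures". For the primary endpoint it offers a two-tailed 95% interval for a proportion by the normal approximation or an exact method, as applicable, without saying when each applies. Section 17.2 tabulates frequency and percentage per response category at the end of Cycle 3. For Stage 1 it evaluates the design by "calculating the frequency and 95% CI of patients with a CR and/or PR at C3D28". For Stage 2 it fits a logistic model adjusted for age, sex and disease type. Section 3.7 mentions exact or nonparametric 95% intervals in SAS. No section names an estimate or interval that uses the two-stage structure.

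**The concern.** The number of patients depends on the early responses. A poor first stage is frozen at 12 patients, while a good one is averaged with 16 more. The proportion at the end of whichever stage is reached is therefore not an unbiased estimate of the response rate, and a one-sample interval does not have its usual guarantee. The logistic model does not help, because its covariates have nothing to do with the stopping rule.

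What is at stake is the reported rate and its interval. Later trials may plan on these, and the SAP itself puts estimation ahead of testing.

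**Working it through.** **Inputs (SAP 3.5 and 4).** n1 = 12, n2 = 16, N = 28; stop if X1 ≤ 6; success if the total is 18 or more; null RR 0.50, alternative 0.75. Let b(x; n, p) be the binomial probability and PET = P(X1 ≤ 6).

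**1. The SAP's own figures.** At p = 0.50, PET = 2510/4096 = 0.613 and the expected sample size is 12 + 16 × (1 − 0.613) = 18.2. The rejection probability, summed over x = 7 to 12 of b(x; 12, p) × P(X2 ≥ 18 − x), is 0.0815 at 0.50 and 0.9017 at 0.75. The SAP gives 0.613, 18.2, 0.081 and 0.902, so all four reproduce.

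**2. Bias of n/N.** Let c be the mean of X1/12 among trials that continue: c = Σ(x = 7 to 12) (x/12) b(x; 12, p) / (1 − PET). The 16 Stage 2 patients are not selected, so their mean is p.

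- Given continuation: bias = (12/28)(c − p).
- Over the whole design, because X1/12 alone has mean p: bias = −(16/28)(1 − PET)(c − p).

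At p = 0.50, c = 1024/1586 = 0.6456 and c − p = 0.1456. Given continuation the bias is 0.4286 × 0.1456 = +0.062. Overall it is −0.5714 × 0.3872 × 0.1456 = −0.032.

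**3. The UMVUE.** For a total s at 28 patients it is Σ C(11, x−1) C(16, s−x) / Σ C(12, x) C(16, s−x), with x from 7 to 12. At s = 18 this is 7,389,954 / 10,934,924 = 67.6%, against 18/28 = 64.3%. The estimator is the average of X1/12 given the total, so its overall bias is zero and its bias given continuation is exactly c − p.

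All entries below except the true RR and PET are in percentage points. RMSE is root mean square error over the whole design, by full enumeration.

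| True RR | PET | n/N bias, whole design | n/N bias, Stage 2 reached | UMVUE bias, Stage 2 reached (c − p) | RMSE n/N | RMSE UMVUE |
|---|---|---|---|---|---|---|
| 0.50 | 0.613 | −3.22 | +6.24 | +14.56 | 11.96 | 13.80 |
| 0.54 | 0.501 | −3.35 | +5.04 | +11.75 | 12.20 | 13.44 |
| 0.60 | 0.335 | −3.03 | +3.41 | +7.96 | 12.36 | 12.59 |
| 0.65 | 0.213 | −2.38 | +2.27 | +5.29 | 12.06 | 11.62 |
| 0.70 | 0.118 | −1.58 | +1.35 | +3.14 | 11.24 | 10.49 |
| 0.75 | 0.054 | −0.86 | +0.68 | +1.59 | 10.00 | 9.28 |

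A search in steps of 0.001 puts the largest overall bias at −3.35 points, at RR 0.538.

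**4. Size for an observed result.** n/N against the UMVUE: 17/28, 60.7% and 65.8%; 18/28, 64.3% and 67.6%; 20/28, 71.4% and 72.4%; 21/28, 75.0% and 75.3%; 22/28, 78.6% for both.

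**5. Coverage of nominal 95% one-sample intervals, applied at whichever stage the trial ends.**

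| True RR | Exact (Clopper-Pearson) | Normal approximation |
|---|---|---|
| 0.50 | 96.3% | 88.6% |
| 0.60 | 97.2% | 95.2% |
| 0.70 | 96.9% | 90.8% |
| 0.75 | 96.4% | 92.6% |
| 0.80 | 95.5% | 90.9% |

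On a fine grid the exact interval never falls below 94.4% (near RR 0.81). Between RR 0.40 and 0.90 the normal approximation falls to about 80% (near 0.895). At 18/28 the one-sample exact interval is 44.1% to 81.4%; an exact interval that orders outcomes over the two-stage design is 44.6% to 82.3%.

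**The case against.** The strongest reply is that the SAP contains no error here. Reporting n/N with an exact interval is common, and accuracy is not the same as unbiasedness. Up to about RR 0.60, where the overall bias is largest, n/N has the smaller root mean square error. The shift is also small against sampling error: 3.3 points at 18/28, inside an exact interval about 37 points wide. This stands, and it is why n/N should remain the main figure.

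A second reply also stands. The UMVUE is no clean cure: every 28-patient report comes from a trial that continued, and there the UMVUE is more biased upward than n/N (14.6 against 6.2 points at RR 0.50; 1.6 against 0.7 at 0.75). Replacing 64.3% by 67.6% as the corrected rate would move the estimate in the drug's favour.

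A third is that an exact method is already allowed and covers adequately. That is true, but the SAP equally allows the normal approximation and does not say which will be used.

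A reader might also infer more than the SAP supports:

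- That the go/no-go decision or its error rates are compromised. They depend on counts and reproduce.
- That the Stage 1 analysis is biased. It has a fixed 12 patients, and as an analysis in its own right x/12 is unbiased.
- That the 6-cycle rate in section 18.2 carries the same bias. The stopping rule acts on 3-cycle response, so these figures do not transfer.
- That the plan overstates efficacy throughout. Over the whole design the bias is downward.

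**Conclusion.** The point holds as a minor one, limited to the final Part B report of 3-cycle response. The simple rate ignores the futility stop. Its bias is downward over the whole design (at most about 3.3 points near RR 0.54, 0.9 at 0.75) and upward once Stage 2 is reached (6.2 points at RR 0.50, 0.7 at 0.75). At the design alternative either bias is under one point. The clearer weakness is the interval: the normal approximation under-covers at most rates examined, while the exact one-sample interval is adequate. Part of that shortfall may be the approximation's own weakness in samples of 12 to 28, not the stopping rule; the two were not separated.

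These figures assume exactly 12 and 28 evaluable patients, the stopping rule applied as written, and independent responses with a common rate. Section 5.2 excludes some treated patients from the ITT set, so the analysed denominators could differ.

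**What to change.** In section 17.2, for 3-cycle response at the end of Part B:

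- Keep n/N as the main figure.
- Replace the choice of interval in 6.5 with a named exact interval, preferably one based on the two-stage sample space. Clopper-Pearson is an acceptable fallback.
- Show the response rate in the 16 Stage 2 patients alone. It is free of Stage 1 selection and contains no Part A patients, since section 3.5 counts those towards Stage 1 only.
- Add the UMVUE as a supplementary figure. Its footnote should say that it removes only the bias over the whole design, that it lies at or above n/N when 28 patients are reached, and that it assumes 12 and 28 evaluable patients.
- Do not apply these corrections to the 6-cycle endpoint in 18.2.

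The cost is a few lines of SAS, a small addition to one table and a footnote. The downside is several supportive figures beside the main one, which readers could confuse without that footnote.

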6.6. COMMON CALCULATIONS

For quantitative measurements, change from baseline (absolute and percentage) will be calculated as:

- Test Value at Visit X – Baseline Value
- $(\text{Test Value at Visit X} - \text{Baseline Value}) / \text{Baseline Value} * 100$

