Document: PPD

Author: PPD

Version Number:

V2.2

Version Date:

21 March 2018

Template No: CS_TP_BS016 – Revision 3

Reference: CS_WI_BS005

Effective Date: 01May2012

Copyright © 2012 Quintiles Transnational Corp. All rights reserved.

The contents of this document are confidential and proprietary to Quintiles Transnational Corp. Unauthorized use, disclosure or reproduction is strictly prohibited.

In the patient listings all the additional ECG data have to be presented as soon as the first one.

- Spleen: Evaluation Date (to be reported only in the patient’s data listings), Imaging Technique (i.e. MRI, CT scan), Results Interpretation (Normal/Abnormal and Not clinically significant/Abnormal and Clinically Significant) and value of the following parameters:
 - o Longitudinal Diameter (cm);
 - o Antero-Posterior Diameter (cm);
 - o Transversal Diameter (cm);
 - o Splenic Volume Index (SVI, in cm³).

Notably, patients with splenomegaly performed the spleen evaluation as per site-specific clinical practice. Therefore, patients with splenomegaly before the treatment start are followed according to institutional guidelines (i.e. MRI, CT scan). The same imaging technique and the same instrument is used on a patient throughout the Study, *when possible*. No spleen evaluation is performed in splenectomised patients.

- Molecular Examination: Sample Collection Date (to be reported only in the patient’s data listings), Sample Accession Number (to be reported only in the patient’s data listings), Back-Up Sample Collection Date (to be reported only in the patient’s data listings), Back-Up Sample Accession Number (to be reported only in the patient’s data listings) and value of the following parameters:
 - o Positivity (Yes/No);
 - o Qualitative Evaluation (Homozygous/Heterozygous);
 - o Quantitative Evaluation (%).
- MPN-SAF Quality of Life Questionnaire: Completion Date (to be reported only in the patient’s data listings) and value (from a score 0 to a score 10) of the following parameters:
 - o Level of fatigue right NOW (i.e. at the completion of the MPN-SAF questionnaire);
 - o USUAL level of fatigue during past 24 hours (i.e. 24 hours before the completion of the MPN-SAF questionnaire);
 - o WORST level of fatigue during past 24 hours (i.e. 24 hours before the completion of the MPN-SAF questionnaire);
 - o Fatigue has interfered with General Activity during the past 24 hours (i.e. 24 hours before the completion of the MPN-SAF questionnaire);

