19. EXPLORATORY OUTCOMES

19.1. PARTS A AND B

The following exploratory parameters will be evaluated using ad-hoc descriptive analysis in **Parts A and B** based on ITT analysis set and PP analysis set:

- The effect of Givinostat on each single response parameter according to the clinico-haematological ELN (for PV and ET) [1] and EUMNET response criteria (for MF) [7]; note that only in case the enrolment in Part A is slow (i.e. < 5 patients enrolled in 3 months), the eligibility for this part of the study could be expanded to all patients with cMPN.
- Effects of Givinostat on PD markers.
- Effects of Givinostat on spleen size in patients with confirmed splenomegaly at baseline.
- Improvement of constitutional symptoms evaluated according to MPN-SAF QOL questionnaire [8, 9] including patients without the symptom of headache, pruritus and microvascular symptoms (i.e MPN SAF Score =0) and number and percentage of patient with symptom score from 0 to 3; from 4 to 6 and more than 7.

Document: PPD

Author: PPD

Version Number:

V2.2

Version Date:

21 March 2018

Template No: CS_TP_BS016 – Revision 3

Reference: CS_WI_BS005

Effective Date: 01May2012

Copyright © 2012 Quintiles Transnational Corp. All rights reserved.

The contents of this document are confidential and proprietary to Quintiles Transnational Corp. Unauthorized use, disclosure or reproduction is strictly prohibited.

- Reduction of the JAK2V617F allele burden, tested by quantitative RT-PCR.
- Reduction of the symptomatic treatment of pruritus in term of dosage and/or days of treatment.

The following exploratory parameters will be evaluated using ad-hoc descriptive analysis in Part B based on ITT analysis set and PP analysis set:

- The preliminary efficacy of Givinostat after 6 cycles of treatment according to the “new” ELN criteria (i.e. revised ELN response criteria) [2]. In all cases, the medical judgment of the Investigator’s is taken into account. In particular, if the Investigator’s clinical response assessment – that takes into account the overall medical judgment of the specific patient’s case - is not in agreement with the exact application of the revised clinico-haematological ELN response criteria , the Investigator’s assessment will supersede the “mathematical” application of these criteria and used for analysis into study report. Also mathematical application of ELN response criteria (not agreed by the medical site team) will be analyzed.

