- The effect of Givinostat on single parameters of the “new” ELN response criteria (i.e. revised ELN response criteria) [2].

The “new” ELN response criteria [2] are detailed in the [paragraph 4.8.7](#) of the Study protocol.

Explorative endpoints will be summarised by descriptive methods based on ITT analysis set and PP analysis set. Default summary statistics and changes from baseline (*where applicable*) to each time point for all parameters will be produced.

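### Percentage change has no rule for a zero baseline, so on 0–10 symptom items the percentage-change summary leaves out every patient who starts symptom-free, including any who worsen

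*SAP*

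**What the plan says.** Section 6.6 (Common Calculations) opens with "For quantitative measurements, change from baseline (absolute and percentage) will be calculated as" and gives two formulas. The first is "Test Value at Visit X – Baseline Value". The second divides that difference by the baseline value and multiplies by 100. Neither is limited to particular measures, and the SAP gives no instruction for a baseline of 0. Section 7.3 says missing data are not imputed.

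Section 10 lists the MPN-SAF questionnaire with "value (from a score 0 to a score 10) of the following parameters". Section 19.1 treats 0 as absence of the symptom: it asks for an analysis "including patients without the symptom of headache, pruritus and microvascular symptoms (i.e MPN SAF Score =0"), and for the "number and percentage of patient with symptom score from 0 to 3; from 4 to 6 and more than 7". For the exploratory endpoints generally it adds: "Default summary statistics and changes from baseline (*where applicable*) to each time point for all parameters will be produced".

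Section 10 also lists basophils, eosinophils and the other differential counts. Section 20.1 asks for actual values and change from baseline by visit for quantitative laboratory data.

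**The concern.** A ratio to baseline does not exist when the baseline is 0. On a scale with a floor of 0, the patients affected are not a random subset. They are exactly those who cannot improve and can only stay at 0 or get worse. Because nothing is imputed, their percentage change stays missing, and the percentage summary describes only patients who had the symptom at the start.

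The study has no control arm, so no comparison group would carry the same distortion and reveal it. A reader of the percentage column could see a clear mean reduction in a symptom whose average level in the whole group had not moved. Differential counts, which can be recorded as 0, raise the same problem on a smaller scale.

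**Working it through.** There is no stated figure in the plan to reproduce on this point, so the check evaluates the section 6.6 formulas directly.

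**Inputs from the SAP:** both formulas (6.6); item range 0 to 10 (10); 0 meaning symptom absent (19.1); no imputation (7.3); 28 patients in the final Part B analysis (4). **Assumed:** the distribution of baseline scores, which the SAP does not give.

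**1. The formulas at baseline 0.**
- Visit score 0: absolute change 0 − 0 = 0; percentage change 0/0, undefined.
- Visit score 3: absolute change 3 − 0 = +3; percentage change 3/0, undefined.

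**2. Patients left in the percentage summary, out of 28.**

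| Assumed share at 0 | Patients at 0 | Evaluable, percentage | Evaluable, absolute |
|---|---|---|---|
| 10% | 3 | 25 | 28 |
| 25% | 7 | 21 | 28 |
| 50% | 14 | 14 | 28 |
| 75% | 21 | 7 | 28 |

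**3. Illustration A (assumed).** Fourteen patients start at 0: 7 rise to 3 and 7 stay at 0. Fourteen start at 4: 7 fall to 1 and 7 stay at 4.
- Mean absolute change: (7×3 + 7×(−3))/28 = 0.0, n = 28.
- Mean percentage change: (7×(−75%) + 7×0%)/14 = −37.5%, n = 14.
- Mean change over mean baseline, all patients: mean baseline is (14×0 + 14×4)/28 = 2, so 0/2 = 0%.

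**4. Illustration B (assumed).** Fourteen start at 0: 4 rise to 3 and 10 stay at 0. Fourteen start at 4 and all fall to 2.
- Mean percentage change: −50%, n = 14; the 4 who worsen are not counted.
- Mean absolute change: (4×3 − 14×2)/28 = −16/28 = −0.57, n = 28.
- Mean change over mean baseline: −0.571/2 = −28.6%.

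**5. What the category counts would show in illustration A.**
- Score 0: 14 patients at baseline, 7 afterwards. The worsening is visible.
- Band 0 to 3: 14 at baseline, then 7 (at 0) + 7 (at 3) + 7 (at 1) = 21. A rise from 0 to 3 stays inside the band, so this count alone looks like improvement.

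**6. A separate property of small integer scores.** A move from 1 to 3 is +200%; from 3 to 1 it is −66.7%. If half the patients do each, mean absolute change is 0 and mean percentage change is (200 − 66.7)/2 = +66.7%. So the percentage mean can also err in the unfavourable direction among patients who are kept.

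**The case against.** The case on the other side is substantial, and much of it stands.

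- **Absolute change is required by the same sentence.** It is defined at baseline 0 and keeps every patient with both values. A reader might infer that symptom-free patients vanish from the symptom analysis altogether; the SAP does not support that. They leave the percentage-change summary only.
- **New symptoms are not hidden from the report.** Section 19.1 counts patients at score 0 for headache, pruritus and microvascular symptoms, section 8 requires all data to be listed, and symptoms reported as adverse events enter the TEAE tables. This stands, with the limits that the category counts cover three symptoms while section 10 lists many more items, and that the lowest band absorbs a rise from 0 to 3.
- **Section 19.1 qualifies its request as applying where applicable, and does not name percentage change.** An undefined ratio could be treated as not applicable. But the SAP does not say when the qualifier operates, and section 6.6 carries no such qualifier.
- **Section 6.6 defines formulas and does not list tables.** Table content is left by section 8 to templates that are not part of the text, so it is an inference that a percentage column will appear for MPN-SAF items. The inference is reasonable from the unrestricted wording, but it is not certain.
- **The reduced n would be visible,** since Appendix 1 makes it a default statistic. That shows fewer patients, but not why.
- **Patients kept in the percentage summary can also worsen.** A patient at 4 can go to 7 and is counted, so the summary is not confined to improvers.
- **The illustrations are constructed.** They show what can happen, not what is likely in this trial.

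**Conclusion.** The point holds as a minor gap in the plan's conventions. Section 6.6 prescribes a calculation that is undefined at a value the SAP itself expects, and the patients lost are those who could not have improved, together with any in whom the symptom appears. The percentage summary can therefore look more favourable than the absolute change beside it: −37.5% against 0.0 in illustration A, −50% against a whole-group ratio of −28.6% in illustration B. Both rest on an assumed 50% share of zero baselines. The actual share is unknown, and at an assumed 10% only 3 of 28 patients would be lost. Favourable distortion is possible, not assured, because the asymmetry of small integer scores can push the other way.

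A reader might go further and doubt the trial's efficacy result. The documents do not support that. The ELN response in section 16.3 uses absence of symptoms at the visit, and the revised ELN response in section 16.11 uses an absolute fall of at least 10 points in the Total Symptom Score. Neither uses a percentage change in symptoms, and no primary or secondary endpoint or Simon decision is affected. What is exposed is exploratory, descriptive output.

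**What to change.** In section 6.6, limit individual percentage change to measures not expected to be zero at baseline, for example HCT, platelets, WBC, splenic volume index and JAK2V617F allele burden. For single MPN-SAF items and differential counts, report absolute change only.

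For the Total Symptom Score, dropping the percentage is more debatable. If a percentage is kept for this or any other score, make absolute change the main summary. Then either state how many patients were excluded for a zero baseline, or give mean change divided by mean baseline on all patients with both values.

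This fits how the SAP already works: the revised ELN criterion for symptoms is in absolute points, while sections 20.4 and 21 use percentage reductions for spleen volume and allele burden.

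Cost: a sentence or two in 6.6 and the removal of some table columns; no new data. The downside is that symptom items would have no individual percentage column.
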